8.3 ADVERSE EVENTS AND SERIOUS ADVERSE EVENTS

8.3.1 DEFINITION OF ADVERSE EVENTS

This protocol uses the definition of adverse event from DHHS Office for Human Research Protections (OHRP): Any untoward or unfavorable medical occurrence in a human subject, including any abnormal sign (for example, abnormal physical exam or laboratory finding), symptom, or disease, temporally associated with the subject's participation in the research, whether or not considered related to the subject's participation in the

8.3.2 DEFINITION OF SERIOUS ADVERSE EVENTS

This protocol uses the definition of serious adverse event from DHHS OHRP: any adverse event that results in death; is life-threatening (places the subject at immediate risk of death from the event as it occurred); results in inpatient hospitalization or prolongation of existing hospitalization; results in a persistent or significant disability/incapacity; results in a congenital anomaly/birth defect; or based upon appropriate medical judgment, may jeopardize the subject's health and may require medical or surgical intervention to prevent one of the other outcomes listed in this definition (examples of such events include allergic bronchospasm requiring intensive treatment in the emergency room or at home, blood dyscrasias or convulsions that do not result in inpatient hospitalization, or the development of drug dependency or drug abuse).

8.3.3 CLASSIFICATION OF AN ADVERSE EVENT

8.3.3.1 SEVERITY OF EVENT

All AEs will be assessed by the PI or co-investigators, if the PI is not available. The following guidelines will be used to describe severity:

- **Mild** – Events require minimal or no treatment and do not interfere with the participant's daily activities.
- **Moderate** – Events result in a low level of inconvenience or concern with the therapeutic measures. Moderate events may cause some interference with functioning.
- **Severe** – Events interrupt a participant's usual daily activity and may require systemic drug therapy or other treatment. Severe events are usually potentially life-threatening or incapacitating. Of note, the term "severe" does not necessarily equate to "serious"]

8.3.3.2 RELATIONSHIP TO STUDY INTERVENTION/EXPERIMENTAL MANIPULATION

All AEs will have their relationship to study procedures, including the intervention, assessed by the PI or co-investigators based on temporal relationship and his/her clinical judgment. The degree of certainty about causality will be graded using the categories below.

- Definitely Related – There is clear evidence to suggest a causal relationship, and other possible contributing factors can be ruled out. The clinical event, including an abnormal laboratory test result, occurs in a plausible time relationship to study intervention administration and cannot be explained by concurrent disease or other drugs or chemicals. The response to withdrawal of the study intervention (dechallenge) should be clinically plausible. The event must be pharmacologically or phenomenologically definitive, with use of a satisfactory rechallenge procedure if necessary.
- Probably Related – There is evidence to suggest a causal relationship, and the influence of other factors is unlikely. The clinical event, including an abnormal laboratory test result, occurs within a reasonable time after administration of the study intervention, is unlikely to be attributed to concurrent disease or other drugs or chemicals, and follows a clinically reasonable response on withdrawal (dechallenge). Rechallenge information is not required to fulfill this definition.
- Not Related – The AE is completely independent of study intervention administration, and/or evidence exists that the event is definitely related to another etiology. There must be an alternative, definitive etiology documented by the clinician.

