2.2 RISK/BENEFIT ASSESSMENT

2.2.1 KNOWN POTENTIAL RISKS

Emotional distress: it is unlikely that the types of questions participants will be asked in this study will result in emotional distress, but we understand that participants may be uncomfortable with answering questions about some aspect of their health or other things about them. To minimize this risk, we will let participants

know they may choose not to answer any study questions and can still be involved in the study. Additionally, participants in the *OA CARE* intervention will have contact information for the study team (e.g. *OA CARE* Navigator) and a YMCA health coach to discuss any concerns.

Breach of confidentiality: we will be collecting some elements of personal health information necessary for the study. To minimize breaches of confidentiality, all data will be stored on a secure UNC server or a UNC IRB approved platform for sharing PHI (with YMCA) and paper information will be stored in locked filing cabinets in the office of a study team member, and only approved study personnel will have access to those data.

Personal health information (e.g. patient name and contact information only) will be shared with YMCA health coaches and personnel conducting the YMCA weight loss and exercise programs. Any information shared between approved UNC study team members and YMCA personnel will be done verbally by phone, by encrypted email or a UNC IRB approved platform for sharing PHI.

For participants in the *OA CARE* intervention, personal health information (e.g. patient name and DOB or MRN) will be shared with the participant's PCP, as part of the brief progress reports sent by the *OA CARE* Navigator. Any information shared between approved UNC study team members (e.g. *OA CARE* Navigator) and the participant's PCP will be done by encrypted email or UNC IRB approved platform for sharing PHI.

Risks of Exercise: Participants in the *OA CARE* intervention will be involved in physical activity programming at the YMCA. This will be tailored to individuals with knee OA. However, exercise programs may be associated with risk of injury, muscle soreness, and joint pain. The risk of sudden death during physical activity is about 1 death per 656,000 hours of physical activity. In general, the risk of these events with moderate physical activity is very low.

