8.3.6 SERIOUS ADVERSE EVENT REPORTING

Once [name] (or a co-investigator) is contacted about a serious adverse event, she / he will make a determination about the reporting requirements in accordance with UNC IRB guidelines. This will include notification of the UNC IRB within 24-hours if a study-related death and within 48 hours if another SAE.

All SAEs will be reported to the NIAMS (through the NIAMS Executive Secretary) within 48 hours of the investigator becoming aware of the event. The SAE Report Form will be completed and the SO's review of the SAE report will be shared with the NIAMS once received.

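### Causality grades in Section 8.3.3.2 cover only the intervention, so injuries in baseline or usual-care assessments cannot be graded related, and an exercise death may fit no grade

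*Combined protocol and SAP*

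**What the plan says.** Section 8.3.3.2 requires each adverse event to have its "relationship to study procedures, including the intervention, assessed by the PI or co-investigators based on temporal relationship and his/her clinical judgment". Section 8.3.4 puts the same item, relation to study procedures, on the adverse event form and starts recording at informed consent.

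Three grades follow.

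- **Definitely Related:** the event has a plausible time relation to giving the intervention and "cannot be explained by concurrent disease or other drugs or chemicals". It adds: "The response to withdrawal of the study intervention (dechallenge) should be clinically plausible". Rechallenge is asked for only if needed.
- **Probably Related:** the event occurs within a reasonable time after the intervention is given and "is unlikely to be attributed to concurrent disease or other drugs or chemicals, and follows a clinically reasonable response on withdrawal (dechallenge".
- **Not Related:** "The AE is completely independent of study intervention administration", and/or there is evidence of another definite cause. In either case the clinician must document a definitive alternative etiology.

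Section 2.2.1 says that "exercise programs may be associated with risk of injury, muscle soreness, and joint pain" and gives a rate for sudden death during activity. It names no risk from the performance tests. Section 8.3.6 requires "notification of the UNC IRB within 24-hours if a study-related death" and 48 hours for any other serious event. Sections 8.3.5 and 8.4.1 each use a threshold of related or possibly related to participation in the research.

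**The concern.** The lead-in and the grades do not cover the same things. The lead-in includes outcome assessments, while the grades mention only the intervention. The participants undergo four physical tests (chair stand, timed up-and-go, march, single-leg stance), some of them before assignment is known and some in an arm that receives no intervention.

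The grades also use drug-trial wording (withdrawal response, rechallenge, pharmacological proof, drugs or chemicals) that fits an exercise and weight-loss programme poorly.

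At stake are the relatedness label on each event, the reporting route where relatedness counts, and the related-event counts that this pilot hands to the larger trial.

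**Working it through.** No formula in the plan is at issue. The check sets each kind of event against each grade and then counts the test administrations affected.

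**Timing.** Sections 5.5 and 6.3 place consent and all baseline assessments before anyone knows the assignment. Section 8.3.4 records events from consent. A fall in a baseline test is therefore a recordable event before any intervention exists. In usual care no study intervention is given during follow-up; Section 4.1 offers the YMCA membership only after follow-up is complete.

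**Count.** Inputs: 60 participants, equally randomized, so 30 per arm (Section 4.1); 4 tests (Section 3); tests at baseline and 12 months only (Sections 3 and 4.1, consistent with the 6-month telephone assessment in Section 8.1). The Section 1.3 table also marks the tests at 6 months; I use the lower count.

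- All administrations: 4 × 60 × 2 = 480.
- Baseline, both arms: 4 × 60 = 240.
- 12 months, usual care: 4 × 30 = 120.
- Administrations that cannot follow any intervention: 240 + 120 = 360, and 360/480 = 75%.

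The other 120 (OA CARE at 12 months) do follow the intervention in time, so a generous reading could admit them.

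**Grades by event.**

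| Event | Definitely Related | Probably Related | Not Related |
|---|---|---|---|
| Test injury, baseline or usual care | No: no intervention given | No: same reason | Literal result, with the test as documented cause |
| Sudden death in exercise | Doubtful: no withdrawal response to judge, and other causes must be ruled out | No: withdrawal response required | Only if another definitive cause is documented |
| Joint pain | Practically closed: OA can explain it | Hard: OA must be an unlikely cause | Only if OA is documented as the definitive cause |
| Exercise sprain or fracture | Possible | Possible: recovery on stopping can count | Only if another definitive cause is documented |

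The joint-pain row rests on Section 5.1: every participant has clinician-diagnosed knee or hip OA with pain of at least 3 out of 10 on most days.

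**Routing.** Section 8.3.3.3 calls an event unexpected if it does not match the risks described. Section 2.2.1 describes none for the tests, so a test injury is arguably unexpected. Relatedness then bears on the 7-day IRB report (Section 8.3.5) and the 48-hour unanticipated-problem report (Section 8.4.2), although each also requires a sign of greater risk.

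**Rarity of the death case.** The documents give no exercise hours. Assuming 2 to 5 hours a week for 52 weeks in 30 people gives 30 × 2 × 52 = 3,120 to 30 × 5 × 52 = 7,800 hours. At the protocol's 1 death per 656,000 hours, the expected number is 3,120/656,000 = 0.0048 to 7,800/656,000 = 0.0119, a chance of about 0.5% to 1.2%.

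**The case against.** A reader might infer that the harms named in Section 2.2.1 can never be graded related, would all default to Not Related, and would be lost to oversight. The documents do not support this.

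- Not Related is not a default, because it needs a documented definitive alternative cause. A death or sprain in a YMCA class without one cannot enter it.
- Knee or hip OA does not explain a sprain or pain in another joint, and exercise pain that eases on stopping is a positive withdrawal response. Exercise injury and some joint pain can therefore reach Probably Related. The lead-in also allows clinical judgment.
- Expected joint pain would not meet the 7-day IRB rule whatever its grade, since that rule also requires the event to be unexpected and to indicate greater risk.
- A death not graded study-related still goes to the IRB within 48 hours, so the loss is at most 24 hours. All serious events go to NIAMS within 48 hours (Section 8.3.6). All events are documented regardless of relationship (Section 8.3.4), and the Safety Officer receives a report of all of them (Section 10.1.6).
- Sections 8.3.5 and 8.4.1 ask about relation to participation in the research, which is broader than the grades and can catch a test injury.

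All of this stands and limits the point. It does not remove the mismatch between lead-in and grades. If the reporting sections catch a test injury that the form records as Not Related, the same event carries two conflicting judgments. Nor would adding a possibly-related grade be enough: if tied to the intervention, it would still exclude assessment injuries.

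**Conclusion.** The point holds as a drafting defect of modest size, worth correcting. As written, an injury in up to 360 of 480 test administrations cannot be graded related and literally falls under Not Related. An unexplained death during exercise may fit no grade, although a study-related death carries the shortest IRB deadline. Both related grades are hard to reach for joint pain.

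The consequence is misclassified relatedness, unclear IRB routing and unreliable related-event counts for the larger trial. It is not unrecorded harm.

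The 360 assumes full attendance and two in-person test visits. It counts opportunities, not events: the documents give no injury rate, so the number of misgraded events cannot be estimated. The death figure rests on assumed exercise hours.

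**What to change.** In Section 8.3.3.2 and on the adverse event form:

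1. In every grade, replace references to giving or withdrawing the intervention with study procedures, including outcome assessments and the intervention.
2. Delete the drug-specific clauses, or make dechallenge and rechallenge apply only where applicable.
3. State that pre-existing knee or hip OA does not by itself exclude a related grade.
4. Reconcile the scale with the possibly-related term in Sections 8.3.5 and 8.4.1, either by adding that level or by stating which grades count as at least possibly related.

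Items 1 and 2 belong together, because a withdrawal response means nothing for a one-off test. The cost is protocol and form wording. The downside is that somewhat more events will be graded related and a few more reports filed.

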8.3.3.3 EXPECTEDNESS

The PI or [name] (co-investigator on the study) will be responsible for determining whether an AE is expected or unexpected. An AE will be considered unexpected if the nature, severity, or frequency of the event is not consistent with the risk information previously described for the study procedures.

8.3.4 TIME PERIOD AND FREQUENCY FOR EVENT ASSESSMENT AND FOLLOW-UP

The occurrence of an AE or serious adverse event (SAE) may come to the attention of study team members during study visits. All AEs, not otherwise precluded per the protocol, will be captured on the Adverse Event Form. Information to be collected includes event description, time of onset, PI or co-investigator's assessment of severity, relationship to study procedures (assessed only by those with the training and authority to make a diagnosis), and time of resolution/stabilization of the event. All AEs occurring while on study will be documented appropriately regardless of relationship. All AEs will be followed to adequate resolution.

Any medical or psychiatric condition that is present at the time that the participant is screened will be considered as baseline and not reported as an AE. However, if the study participant's condition deteriorates at any time during the study, it will be recorded as an AE.

Changes in the severity of an AE will be documented to allow an assessment of the duration of the event at each level of severity to be performed. Documentation of onset and duration of each episode will be maintained for AEs characterized as intermittent.

The Project Coordinator will record events with start dates occurring any time after informed consent is obtained until 7 (for non-serious AEs) or 30 days (for SAEs) after the last day of study participation.

Participants are identified in the EMR as a study participant and for each AE/SAE occurrence, research team members will receive an alert through EMR. AEs or SAEs may also be reported to study physical therapist during the course of intervention visits. Events will be followed for outcome information until resolution or stabilization.

8.3.5 ADVERSE EVENT REPORTING

Once [name] (or a co-investigator) is contacted about the adverse event, she / he will make a determination about the reporting requirements in accordance with UNC IRB guidelines.

The PI or a co-investigator will report any AEs to the UNC IRB that suggest new or increased risk to participants or others within 7 calendar days of when the PI became aware of the information. New or increased risk is defined as any incident, experience, outcome, or new information that are (1) unexpected, (2) related or at least possible related to participation in the research, and (3) indicates that subjects or others are at a greater risk of harm (including physical, psychological, economic, legal, or social harm)

For AEs that are not related to participation in the research and do not suggest new or increased risks to the participant, these will be reported to NIAMS on the bi-annual safety report submitted to the SO

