8.4. UNANTICIPATED PROBLEMS

8.4.1 DEFINITION OF UNANTICIPATED PROBLEMS

This protocol uses the definition of Unanticipated Problems as defined by the Office for Human Research Protections (OHRP). OHRP considers unanticipated problems involving risks to participants or others to include, in general, any incident, experience, or outcome that meets all of the following criteria:

- (1) Unexpected (in terms of nature, severity, or frequency) given (a) the research procedures that are described in the IRB-approved research protocol and informed consent document; and (b) the characteristics of the participant population being studied;
- (2) Related or possibly related to participation in the research. *Possibly related* means there is a reasonable possibility that the incident, experience, or outcome may have been caused by the procedures involved in the research); and
- (3) Suggests that the research places participants or others at a greater risk of harm (including physical, psychological, economic, or social harm) than was previously known or recognized.

OHRP recognizes that it may be difficult to determine whether a particular incident, experience, or outcome is unexpected and whether it is related or possibly related to participation in the research. OHRP notes that an incident, experience, or outcome that meets the three criteria above generally will warrant consideration of substantive changes in the research protocol or informed consent process/document or other corrective actions in order to protect the safety, welfare, or rights of participants or others.

The following corrective actions or substantive changes that could be considered in response to an unanticipated problem include:

- Changes to the research protocol initiated by the investigator prior to obtaining IRB approval to eliminate apparent immediate hazards to subjects;
- modification of inclusion or exclusion criteria to mitigate the newly identified risks;
- implementation of additional procedures for monitoring subjects; suspension of enrollment of new subjects;
- suspension of research procedures in currently enrolled subjects;

- modification of informed consent documents to include a description of newly recognized risks;
- provision of additional information about newly recognized risks to previously enrolled subjects.

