8.4.2 UNANTICIPATED PROBLEMS REPORTING

All UPs will be reported to UNC IRB within 48 hours of the PI becoming aware of the event. All UPs will be reported to the NIAMS and the SO (through the NIAMS Executive Secretary) within 48 hours of the PI becoming aware of the event.

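### A non-serious adverse event that is also an unanticipated problem has two IRB deadlines (7 days and 48 hours) and two recipient lists, and the causality scale has no grade for a possible link

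*Combined protocol and SAP*

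**What the plan says.** Section 8.3.5 (Adverse Event Reporting) requires the PI or a co-investigator to report AEs that suggest new or increased risk to the UNC IRB "within 7 calendar days of when the PI became aware of the information". Such risk has three elements: the event is unexpected, it is "related or at least possible related to participation in the research", and it points to a greater risk of harm. The IRB is the only recipient named for these events. The section mentions NIAMS only for the bi-annual safety report, and there the wording is "For AEs that are not related to participation in the research and do not suggest new or increased risks to the participant".

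Section 8.4.1 (Definition of Unanticipated Problems) also has three elements: unexpected, "Related or possibly related to participation in the research", and suggestive of a greater risk of harm than was known before. It explains a possible relationship as a "reasonable possibility that the incident, experience, or outcome may have been caused by the procedures involved in the research". It adds that a small subset of AEs will meet the definition. Section 8.4.2 then states: "All UPs will be reported to UNC IRB within 48 hours of the PI becoming aware of the event". It continues: "All UPs will be reported to the NIAMS and the SO (through the NIAMS Executive Secretary) within 48 hours".

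Section 8.3.3.2 has the investigators grade causality using three listed categories: Definitely Related, Probably Related and Not Related. Probably Related requires that "the influence of other factors is unlikely". Not Related requires the clinician to document a definitive alternative cause.

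**The concern.** One event can fall under both reporting rules, and the rules differ on when to report and to whom. The protocol does not say which governs. Someone working from the AE section would find a 7-day limit and one recipient, with no sign that a 48-hour rule and two further recipients also apply. The practical risk is that NIAMS and the Safety Officer are told late, or not told promptly at all, about the AEs that may call for a change to the study.

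The causality scale raises a separate, smaller problem. Both rules cover events that are only possibly related, but the scale cannot record that judgement. Such an event may be entered as Not Related. If that grade is then used in the reporting decision, the event fails the relatedness test in 8.3.5 and drifts towards the bi-annual route.

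**Working it through.** The protocol gives no figure to reproduce here. The check sets the sections side by side, with one subtraction.

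**Step 1. Do the two definitions cover the same event?**

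| Test | 8.3.5 | 8.4.1 |
|---|---|---|
| Expectedness | unexpected | unexpected, in nature, severity or frequency |
| Relationship | related or at least possibly related | related or possibly related |
| Harm | greater risk; physical, psychological, economic, legal or social | greater risk than previously recognised; physical, psychological, economic or social |

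The definitions differ at the margins. Section 8.3.5 adds legal harm. Section 8.4.1 adds the comparison with what was known before, but 8.3.5 is itself about new or increased risk. For the four kinds of harm common to both, the overlap is essentially complete, and 8.4.1 itself says that some AEs are unanticipated problems.

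**Step 2. How far apart are the deadlines?** Both run from PI awareness, in 8.3.5 of the information and in 8.4.2 of the event. Assume that these are the same moment.

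- 8.3.5: 7 × 24 = 168 hours
- 8.4.2: 48 hours
- Conflict window: 168 − 48 = 120 hours = 5 days
- Share of the 8.3.5 window: 120 / 168 = 0.714, or 71%

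A report on days 3 to 7 meets 8.3.5 and breaches 8.4.2. A report within 48 hours meets both limits.

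**Step 3. Who is told?** Section 8.3.5 names one recipient for this event, the IRB. Section 8.4.2 names three: the IRB, NIAMS and the Safety Officer.

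**Step 4. Which events are affected?** Section 8.3.6 sets IRB notice of a serious AE at 24 hours for a study-related death and 48 hours otherwise, with NIAMS told within 48 hours. The deadline conflict is therefore confined to non-serious AEs meeting all three tests. The documents give no expected number of these.

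**Step 5. Can the causality scale record a possible link?** Take an event with a reasonable but unproven link and a competing explanation that is neither unlikely nor established.

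- Definitely Related fails, because other contributing factors cannot be ruled out.
- Probably Related fails, because the influence of other factors is not unlikely.
- Not Related fails, because there is no documented definitive alternative cause.

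No grade fits. Joint pain after YMCA exercise shows the gap: section 2.2.1 lists joint pain as an exercise risk, and osteoarthritis is a competing cause. As an expected event it would not ordinarily be an unanticipated problem, so it illustrates the grading gap and not the deadline conflict.

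**The case against.** The strongest reply is that the two rules can be read together. Section 8.4.2 applies to all unanticipated problems without exception, so an AE that is one follows the 48-hour rule, and 7 days is an outer limit. Section 8.3.5 does not say that only the IRB is to be told, so the recipient lists add up. It also opens by leaving reporting requirements to a determination under UNC IRB guidelines. The report is assigned to the PI or a co-investigator, who can be expected to know both sections. On this reading only a cross-reference is missing, in a 60-participant study that the protocol calls minimal risk.

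Much of this stands. Compliance with both rules is possible, few events should qualify, and the 120 hours measures the gap between two limits, not harm to anyone. But the combined reading has to be supplied by the reader. Each section states its own IRB limit and neither gives precedence. IRB guidelines, which are not in the documents, might settle the IRB deadline but would not obviously settle notice to NIAMS and the Safety Officer.

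On causality, it is fair to say that the reporting triggers are not formally tied to the grade. The investigator can apply the 8.4.1 meaning directly, 8.3.4 has all AEs documented whatever their relationship, and 10.1.6 gives the Safety Officer a report of all AEs, biannually or on request. What is lost is the accuracy of the grade. That matters because 8.3.4 requires the relationship to be recorded, and 8.3.5 words its bi-annual NIAMS reporting around relatedness.

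**Conclusion.** Both parts hold. For a non-serious AE that is unexpected, at least possibly related and risk-raising, the protocol states two IRB limits 120 hours apart and names one recipient in one place and three in the other, with no rule of precedence. This assumes that both clocks start together and that the harm is of a kind covered by both definitions. Separately, the three-grade causality scale has no place for an event that is only possibly related, although both reporting rules include such events.

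The scope is narrow: serious AEs are outside the deadline conflict, and no endpoint or analysis is affected. It is still a contradiction in safety reporting that should be corrected. The documents do not show which deadline is intended, and this review does not choose one.

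**What to change.** - **Reporting.** Add a cross-reference in 8.3.5 to 8.4.2, so that any AE meeting the three tests has one deadline and one recipient list. Confirm both with the IRB and make the two sections agree.
- **Causality.** Add a Possibly Related grade to 8.3.3.2 and to the AE form, defined by the meaning that 8.4.1 already gives: a reasonable possibility that the research procedures caused the event.

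The cost is one cross-reference, one definition and one extra option on the form.
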